3 LIST OF ACRONYMS AND ABBREVIATIONS

AIDS	Acquired Immunodeficiency Syndrome
AIM	Acceptability of Intervention Measure
ANOVA	Analysis of Variance
BSC	Bwaila STI Clinic
EMR	Electronic Medical registry
FGD	Focus Group Discussion
FGHF	Fogarty Global Health Fellowship
FIM	Feasibility of Intervention Measure
GHE	Group Health Education
HCWs	Healthcare Workers
HIV	Human immunodeficiency Virus
HTS	HIV testing Services
IDI	In-depth Interview
IHE	Intensified Health Education
LDH	Lilongwe District Hospital
LMICs	Low and Middle-Income Countries
MoH	Ministry of Health
NHSRC	National Health Sciences Research Ethics Committee
NIRN	National Implementation Research Network
ODK	Open Data Kit
PEPFAR	President's Emergency Plan For AIDS Relief
PrEP	Pre-Exposure Prophylaxis
RITE	Re-imbursement, Intensified health education, cell phone Tracing and Escorts
SE Africa	Southern and Eastern Africa
SEM	Structural Equation Modelling
SMS	Short Messaging Service
SOC	Standard of Care
STIs	Sexually Transmitted Infections
UNAIDS	The Joint United Nations Program on HIV and AIDS
UNC IRB	University of North Carolina Institutional Review Board
VMMC	Voluntary Medical Male Circumcision
WHO	World AIDS Organization
WITS HREC	University of Witwatersrand Human Research Ethics Committee

4 DEFINITIONS

Acceptability: the perception among men and healthcare workers that the adaptable RITE intervention is agreeable, palatable and satisfactory.

Appropriateness: the perceived fit of the adaptable RITE intervention to address the problem of low uptake of VMMC among men and healthcare workers.

Clinic escort: the act of escorting/accompanying a participant interested in VMMC from the STI clinic to the VMMC clinic to ensure linkage to care.

Contamination: a situation where the study population become exposed to more than one intervention component

Feasibility: the extent to which the adaptable RITE intervention will be successfully carried out at Bwaila STI clinic.

Intensified health education: consistent and setting-specific education on VMMC incorporated into the routine STI/HIV health education provided at Bwaila STI clinic.

Interference: a scenario where other stakeholders implement an intervention(s) aimed to scale-up the uptake of VMMC at the study sites which may affect attribution.

Seasonality: periodic variation in the uptake of VMMC with calendar time

SMS reminder tracing: the act of reminding participants with a VMMC appointment about their date of procedure through short messaging service.

Time-to-uptake: the number of days from the day a participant is offered VMMC to the day they undergo VMMC

Transport reimbursement: refunding money used for transportation to Bwaila district hospital for participants who undergo VMMC using standard Malawi government rates.

Uptake: the action of undergoing VMMC.

5 INTRODUCTION

5.1 Background Information

Human Immunodeficiency Virus (HIV) infection remains a huge public health burden globally. In 2018, approximately 36.9 million people were living with HIV infection and there were about 940,000 AIDS-related deaths worldwide [1]. In the past decade, the decline in new HIV infections among adults slowed down and has remained static at about 1.9 million people per year world-wide in recent years [2]. Southern and Eastern (SE) Africa is the world's most affected region, accounting for 44% of new infections and with about 52% of the people living with HIV residing in this region [3]. While some countries in the region, such as Uganda and Mozambique, have made great progress in reducing new HIV infections in adults, some, such as Lesotho have been less successful [4]. In Malawi, the HIV prevalence among adults was 9.2% in 2018 [5]

In 2014, the Joint United Nations Program on HIV and AIDS (UNAIDS) developed the fast-track target to reduce the number of global new annual HIV infections among adults to fewer than 200,000 and, in 2016, revised the target to end AIDS as a public health threat by 2030 [2]. As part of achieving this ambitious global plan, UNAIDS called for scale-up of combination prevention strategies [2]. Combination prevention approaches promote simultaneous use of complementary biomedical, behavioral and structural strategies and can be implemented at individual, community and population levels as they are amenable to setting-specific factors such as culture, infrastructure and populations most affected by HIV [2]. One of the immediate goals for UNAIDS is to ensure access to combination prevention options which include pre-exposure prophylaxis, voluntary medical male circumcision (VMMC), harm reduction and condom use to

at least 90% of people by 2020 [6]. However, as the number of new HIV infections remains static at 1.9 million people per year [1], progress in HIV prevention is off-track, highlighting the need for innovative ways to scale-up combination prevention strategies.

One of the existing biomedical prevention methods that is under-utilized in SE Africa is voluntary medical male circumcision [3]. The coverage of VMMC in the region remained below 30% in 2016 compared to other HIV prevention methods such as condom use (83%), HIV testing (76%) and prevention of mother-to-child transmission (89%) [2].

In the mid-2000s, VMMC was confirmed to reduce the risk of HIV transmission by 60% during unprotected heterosexual sex [7]. Three randomized controlled trials in South Africa, Kenya and Uganda contributed overwhelming evidence that VMMC significantly lowers the rate of HIV transmission [8–10]. Consequently, in 2007 the World Health Organization (WHO) and UNAIDS recommended VMMC as a part of the comprehensive HIV prevention strategy for high HIV prevalence and low male circumcision areas – where the greatest public health impact would be realized [11]. As a result, 15 countries in SE Africa, including Malawi, were identified by UNAIDS and WHO as priority countries for expansion of VMMC activities for HIV prevention [2].

Since 2008, VMMC activities for HIV prevention increased in SE Africa [3]. This resulted in an increase in cumulative VMMCs performed between 2008 and 2015. However, by 2016, the coverage of VMMC remained below 30% across the region [3]. In 2016, UNAIDS and WHO set a target to reach 90% of males of 10-29 years in the priority countries with VMMC by 2021 - a target not easy to reach [2].

In Malawi, after several years of debate, VMMC was adopted as a HIV prevention strategy in

2012. The prevalence of male circumcision among men aged 15-49 years was 28% in 2016 with only 9% being medical circumcision and 18% traditional circumcision [12]. This coverage is far below the 80% regional target and 60% national target [2,12]. In fact, Malawi has one of the lowest VMMC coverage rates among the priority countries [13]. Since 2008, there has been an increase in the number of VMMCs performed through the Ministry of Health (MoH) VMMC program with support from the President's Emergency Plan for AIDS Relief (PEPFAR), however coverage and uptake have remained low. About 157,504 circumcisions were performed between 2008 and 2014 representing 8% of the target population [14]. Lilongwe, the capital city of Malawi also a PEPFAR supported district, has one of the highest HIV prevalence rates and lowest national circumcision coverage rates (14% in 2015) [2].

Despite the low coverage and uptake of VMMC, early acceptability studies in Malawi showed that VMMC was acceptable among certain communities [15] and recent data show favorable results across different settings in Malawi [16,17]. Some of the most common factors reported to deter men from undergoing VMMC in Malawi include low HIV risk perceptions, especially among older men; fear of pain; lack of support from partner or parent or peers; a preference for traditional circumcision as part of culture in some communities; fear of complications including bleeding, impotence and infections; religious influence; costs associated with accessing VMMC; lack of knowledge on medical benefits of VMMC including myths and misconceptions and unwillingness to be attended to by female healthcare providers [16,18–23].

Carrasco and colleagues conducted a study in three high HIV prevalence districts in southern Malawi and found that only 8% of high-risk group of men accessed VMMC services [13]. Men attending STI clinics are a high-risk population because sexually transmitted infections (STIs) increase the risk of HIV acquisition and transmission by three-fold or more [24]. STI clinics in

Malawi have high HIV prevalence estimated at around 19% in 2018 [25] and low VMMC rates 28% [26]. In the STI setting, VMMC is not only protective against HIV but also against curable STIs [24]. In view of this background, increasing the coverage and uptake of VMMC in men attending STI clinics could potentially result in a greater impact, making STI clinics an ideal setting for scale-up of VMMC services.

Therefore, in an attempt to address the factors outlined above in order to increase the demand and uptake of VMMC, this study proposes to use an adaptable intervention comprising four intervention components that include transport reimbursements (**R**), intensified health education (**I**), SMS reminder tracing (**T**) and clinic escorts (**E**) – coined as the **RITE** intervention. This intervention was developed based on literature. Details of the intervention have been outlined in the methods section below.

5.2 Problem statement

Since the inception of VMMC, many countries have fallen below targets resulting in the new fast-track target - to have 90% of males of 10-29 years in priority countries circumcised by 2021 [2]. To achieve this goal, there is need to intensify current efforts and to develop novel strategies in the implementation of VMMC programs [4]. In Malawi, despite efforts to increase the supply of VMMC services in order to improve national coverage, the demand/uptake has remained low [2]. The low demand/uptake poses a great risk of continued HIV and STI transmission.

UNAIDS recommends prioritizing VMMC to sub-populations (for example by age or risk level) to maximize its impact and efficiency [2]. One such sub-population is men attending STI clinics who may have symptomatic or asymptomatic STIs. The Malawi STI guidelines stipulate that VMMC should be offered to all male uncircumcised STI clients, however, this population has

not been prioritized [27]. Recently, the Malawi VMMC program introduced a mobilizer to STI clinics who conduct health education talks on VMMC every morning, however MC rates have continued to remain low – estimated at 28% [26]. Finally, the lack of knowledge on medical benefits of VMMC among the general population may translate to a lack of knowledge on the same among men at STI clinics, which may pose as a major barrier for the demand for VMMC in this population [16,18–23]. In addition, time from when men are offered VMMC to when they undergo the procedure is not well studied and documented. We hypothesize that uptake of VMMC will be higher within the first seven days of exposure to intervention. Obtaining insight on this would help with the design of interventions and programs and the period needed to sustain intervention or program exposure.

Justification

Despite VMMC being a primary focus of the HIV prevention in Malawi, uptake has been far below expected levels due to varied reasons since its inception in 2012. Some of the common reasons include perception of low HIV risk especially among older men, lack of knowledge on medical benefits of VMMC, lack of support from partners or parents or peers and fear of pain and complications of VMMC. Further, the uptake of VMMC has been much lower in men presenting to health facilities with STIs – a high-risk group for HIV acquisition and transmission. Currently, published data on coverage and uptake of VMMC among STI clients in Malawi is unavailable. Further, there are no registered trials of novel strategies for improving the implementation of the VMMC program among men attending STI clinics in Malawi. This study aims to evaluate the RITE implementation intervention implemented systematically to increase the demand and uptake of VMMC among men attending a STI clinic in Lilongwe Malawi.

5.3 The conceptual framework

Creating demand for VMMC is a key strategy for improving uptake in the priority countries [2].

This study is anchored on the theory that knowledge is an integral component of perceptions and that perceptions are a major determinant of behavioral change [28].

Overall, our framework aims to increase the demand of VMMC by first developing insight on the factors that influence decision making whether or not to undergo VMMC among men attending STI clinics then develop health education content and to inform possible modification of the linkage-to-VMMC approaches based on these factors.

Sgaier et al's (2015) framework for demand generation [29], Maibvise and Mavundla (2019) model to promote the uptake of male circumcision [28] and the National Implementation Research Network (NIRN) stages of implementation (2010) by Fixsen et al [30] form the conceptual framework for this study (Figure 1). Sgaier et al's framework focuses on developing insight into reasons for low demand for VMMC in subpopulations and developing innovative solutions to the identified reasons and Maibvise et al's model conceptualizes the processes through which health care workers can promote the uptake of VMMC as an HIV-preventive method in high HIV prevalence and low circumcision settings. NIRN provides a set of systematic stages through which the implementation of an intervention should follow.

The main features of the framework are related and are in two iterative steps. The two steps illustrate the transition from improved demand towards improved uptake of VMMC.

Steps of the conceptual framework: The overall approach for this study will be in two steps detailed below:

Step A: Insight Development, Exploration and Installation–

The aim of this step is to develop insight on the factors that influence decision making for circumcision among men in STI clinics. This step was guided by Sgaier et al's, and Maibvise and Mavundla's frameworks; and have been combined with the exploration and installation stages of the NIRN framework.

To develop insight, we will conduct key stakeholder consultations. Key stakeholders will include the ministry of health VMMC program, the Centers for Disease Control (CDC) VMMC program, Population Services International (PSI) VMMC program, Johns Hopkins Program for International Education in Gynecology and Obstetrics (Jhpiego) and healthcare workers at Bwaila VMMC clinic and STI clinic. The aim of the meeting will be understand the views of men of VMMC from the experts and identify the best way to conduct health education and the appropriate content to include in health education material in a STI clinic setting. This is the NIRN 'exploration' stage.

The identified factors will inform the development of health education material for demand creation and the best way to deliver the material. Education sessions will be interactive to allow a continuum of insight development and improvement processes. Sustained education is aimed to create a sustained social support system for the men, from peers and sexual partners. Healthcare workers and Bwaila STI clinic and VMMC clinic will be trained on the final intervention. This is the NIRN 'installation' stage.

[figure not shown]

Figure 1: Conceptual Framework for Scale-up of VMMC - Adapted from Maibvise, 2019, Sgaier 2015 and Fixsen 2010

Step B: Linkage to care, Initial Implementation and Full Implementation

The aim of this step is to improve uptake of VMMC by improving linkage and access to VMMC.

Healthcare workers (HCW) at the STI clinic will facilitate access and utilization of safe VMMC services using different intervention components. However, before fully implementing the intervention, we will pilot the intensified health education among men and healthcare workers

delivering the education. This is the ‘initial implementation’ stage of the NIRN framework. Once our intervention is piloted, we will proceed with full implementation, the final NIRN stage.

5.4 Study Objectives

5.4.1 Main Aim

The aim of this study is to evaluate the RITE intervention for improved uptake of VMMC among men attending Bwaila STI clinic in Lilongwe, Malawi between May 2020 and October 2020.

5.4.2 Specific objectives

1. To compare uptake of voluntary medical male circumcision between the RITE intervention and the standard of care among men attending Bwaila STI clinic in Lilongwe Malawi
 - a. To compare time-to-uptake of voluntary medical male circumcision between the RITE intervention and the standard of care among men attending Bwaila STI clinic in Lilongwe Malawi
 - b. To assess factors affecting uptake of voluntary medical male circumcision among men attending Bwaila STI clinic in Lilongwe Malawi
2. To develop STI clinic setting-specific voluntary medical male circumcision educational material at Bwaila STI clinic in Lilongwe Malawi
3. To assess the acceptability, appropriateness and feasibility of the RITE intervention among men and healthcare workers at Bwaila STI clinic in Lilongwe, Malawi.

- a. To assess the acceptability and appropriateness of the RITE intervention among men at Bwaila STI clinic in Lilongwe, Malawi

6 METHODOLOGY

6.1 Study design

This is a pragmatic, pre- and post-interventional quasi-experimental study combined with a prospective observational study design. The primary aim is to determine the effectiveness of the RITE intervention in increasing the uptake of VMMC at Bwaila STI clinic. The implementation science aim is to determine the potential utility (feasibility, acceptability and appropriateness) of RITE intervention in an STI clinic setting [31]. We will use a sequential mixed methods approach, starting with formative qualitative study to refine the proposed intervention (RITE), followed by a pragmatic, mixed-methods quasi-experimental study with one pre-exposure and four distinct exposure groups [7]. This stand-alone intervention will be implemented at a practical STI clinic setting without random allocation to the intervention. We will observe for the standard of care (SOC) in the pre-intervention phase and introduce our intervention in a step fashion of different intervention combinations with four different intervention groups. This approach will allow us to assess the effect of the intervention while assessing the effect of different combinations of the intervention components, building up to the full intervention. Since the STI clinic is an outpatient clinic and STIs are generally acute infections that resolve quickly with treatment, it is not possible to randomize intervention components and follow the same participants over time as a cohort hence the different exposure groups. The key outcome of interest, VMMC uptake, will be measured at the VMMC facility.

6.2 Study setting

The study setting is the Bwaila STI Clinic (BSC) and Bwaila VMMC clinic at Bwaila District Hospital (BDH). BDH is a public secondary level facility in Lilongwe and the only facility offering specialized STI care situated in a busy central town area of the Lilongwe district. Approximately 80 patients visit BSC per day. The VMMC clinic and BSC are about 300 meters apart within the BDH campus. Twenty (20) people comprising nurses, clinicians, HIV testing services (HTS) counsellors, receptionists and support staff run BSC. As standard of care, all STI patients at BSC receive group health education (GHE) and are offered opt-out provider initiated HIV testing as standard of care, before receiving care for their STIs. We propose to integrate intensified health education to the GHE. About two to three GHE sessions are conducted per day with different cohorts of patients based on their time of arrival at the clinic however only one GHE includes education on VMMC. The clinic receptionist assisted by a nurse or counsellor conducts GHE. The first GHE session includes a mobilizer from the VMMC clinic who conducts an educational talk on VMMC every morning at the STI clinic and refers men to the VMMC clinic using referral slips. The additional GHE sessions do not have educational talks by the mobilizer. We will train the clinic receptionist, counselors, nurses and the mobilizer to conduct intensified health education. As standard of care, uncircumcised men with STIs are supposed to be offered VMMC at the STI clinic by clinicians however this is not reinforced. Data on demographics, HIV testing and treatment, sexual history and STIs are collected routinely through an electronic medical registry.

The VMMC clinic has a director, administrator, program officers, clinicians (male and female), nurses (both male and female), data clerks, mobilizers and support staff. A team consisting of one clinician, an assisting nurse and other support staff conduct circumcisions. Circumcisions are

done at the VMMC clinic and in the community through outreach clinics and mobile vans. Data such as demographics, referral source, date and outcome of VMMC are recorded in registers. We will use these registers to track men referred from the STI clinic who will undergo circumcision. Men attending the STI clinic may either be index cases (symptomatic) or sexual partners (symptomatic or asymptomatic). Men with symptomatic STIs will not undergo VMMC on the same day of their STI clinic visit until they complete treatment for their current STI.

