Clinic escorts will be the act of escorting/accompanying a participant interested in VMMC from the STI clinic to the VMMC clinic to ensure linkage to care. We propose to use clinic escorts who will accompany men interested in VMMC from the STI clinic to the VMMC clinic to ensure that men are not lost in transit. Men may either undergo same day VMMC (if asymptomatic) or have an appointment for VMMC on a later date if symptomatic or if they have other viable reasons. Escorting patients is beneficial in linkage and retention in care and is policy in varied clinical settings [32]. Clinic escorts will be data clerks and clinic aides.

SMS Tracing (T)

SMS reminder tracing will be the act of reminding participants with a VMMC appointment about their date of procedure through short messaging service. This PhD study proposes to use SMS tracing to remind men who could not have same day VMMC of their appointment for VMMC. The content and frequency of the SMS messages will be guided by the findings from formative research however we have included a modifiable guide of the messages. Cell phone tracing is also a proven strategy for minimizing loss to follow-up and improving retention [33–35]

Transport Reimbursement (R)

Transport reimbursement will be refunding money used for transportation to the Bwaila district hospital for participants who undergo VMMC using standard Malawi government rates.

Transport reimbursement equivalent to US\$10 as stipulated by the National Health Sciences Research Ethics Committee (NHSRC) in Malawi, will be offered to all men who will undergo VMMC on the day of the procedure to minimize the opportunity cost. Incentives also have been shown to improve many medical outcomes [40, 41]. Eligible men will receive transport reimbursement when they undergo VMMC. Men who cannot have same day circumcision will receive a coupon to present on the day of the procedure for reimbursement. Documentation of the VMMC procedure will be confirmed in the VMMC clinic's procedures register before payment.

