6.2 Data Collection

Overall, we will collect demographic characteristics for our study population. Among men accessing STI care, we will collect demographic data such as age, marital status, educational status and socioeconomic status. Additional data collected may include sexual history, HIV and ART status. Data will be collected using the routine electronic medical registry at Bwaila STI clinic and exported into a Microsoft Excel spreadsheet.

Objective 1: To compare uptake of voluntary medical male circumcision between the standard of care and the different combinations of the RITE intervention among men attending Bwaila STI clinic in Lilongwe Malawi

Uptake in this study will be the action of undergoing VMMC. Uptake of the intervention will be measured for each implementation block. Data on demographic characteristics including contact information, HIV history, sexual history and STI data will be collected for all participants from

the STI clinic using a routine clinical form through the electronic medical registry (EMR) (Appendix 2). We will collect data on the number of uncircumcised men offered VMMC and the number of men referred to the VMMC clinic from the STI clinic using study specific data collection form (Appendix 3). In addition the number of men who underwent VMMC will be collected from routine VMMC clinic registers using a study specific data collection form (Appendix 4). Data clerks and the VMMC mobilizer will collect these data on a daily basis from both clinics. SMS tracing attempts will be collected separately on a study-specific SMS tracing form (Appendix 5). The content of the SMS will be designed during the pre-test but we have included a draft of what the content may include (Appendix 5). The data will be collected and collated daily by a data clerk. Data will be entered into a Microsoft Excel spreadsheet by a data assistant.

Objective 1a: To compare time-to-uptake of voluntary medical male circumcision between the pre- and post-intervention periods among men attending Bwaila STI clinic in Lilongwe Malawi

Time-to-uptake will be the number of days from the day a participant is offered VMMC to the day they undergo VMMC. Data clerks will collect data on the date the participant is offered VMMC from the STI clinic using a study-specific data collection form (Appendix 3) while the date the participant undergoes VMMC will be collected from routine VMMC clinic registers on a daily basis and entered into Microsoft Excel.

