Uptake will be calculated as a proportion - the number of men who will undergo VMMC divided by the number of uncircumcised men offered VMMC at the STI clinic. Uptake will be calculated for each implementation block. Uptake for each block will be compared against SOC using Student's T-test at $\alpha=0.05$ significance level and 95% confidence interval, assuming normal distribution.

Objective 1a: To compare time-to-uptake of voluntary medical male circumcision between the standard of care and intervention period among men attending Bwaila STI clinic in Lilongwe Malawi

Time-to-uptake of VMMC will be calculated as the number of days taken for an individual to undergo circumcision at the VMMC clinic from the day they were offered circumcision at the STI clinic. To compare time-to-uptake between SOC and the intervention blocks, we will conduct time-to-event analysis to estimate duration to circumcision and Kaplan Meier curves will be plotted and compared between SOC and implementation blocks. We will also study factors affecting time-to-uptake using cox regression.

Objective 1b: To assess factors affecting uptake of voluntary medical male circumcision among men attending Bwaila STI clinic in Lilongwe Malawi

We will assess factors affecting uptake of VMMC using logistic regression modeling. We will use univariate models to assess association. Covariates with $P<0.05$ and those based on expert knowledge of this topic will be fit into multivariate logistic regression models to control for confounders.

Objective 2: To develop STI clinic setting-specific voluntary medical male circumcision educational material at Bwaila STI clinic in Lilongwe Malawi

We will use thematic analysis approach for qualitative analysis of the consultative meeting notes. The notes will be coded and salient themes will be identified. The content and delivery methods will be deduced from the salient themes.

Objective 3: To assess the acceptability, appropriateness and feasibility of the adaptable RITE intervention among men and healthcare workers at Bwaila STI clinic in Lilongwe, Malawi.

We will use mixed methods to assess acceptability, appropriateness and feasibility. For acceptability, appropriateness and feasibility quantitative surveys, these outcomes will be

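### Uptake is defined without a venue limit, but the plan does not make clear that outreach and mobile-van circumcisions are captured; if they are not, a shift of venue from block two onward could look like higher uptake

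*Combined protocol and SAP*

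**What the plan says.** - **Definition (section 4).** "Uptake: the action of undergoing VMMC". Time-to-uptake runs from the offer to the procedure. Neither definition names a venue.
- **Where the service operates (section 6.2, Study setting).** Circumcisions are "done at the VMMC clinic and in the community through outreach clinics and mobile vans". The same paragraph says that registers record referral source, date and outcome, and adds: "We will use these registers to track men referred from the STI clinic who will undergo circumcision".
- **Where the outcome is measured (section 6.1, Study design).** "The key outcome of interest, VMMC uptake, will be measured at the VMMC facility".
- **Source of the numerator (section 6.2, Data Collection, Objective 1).** The "number of men who underwent VMMC will be collected from routine VMMC clinic registers".
- **Primary formula (Data Analysis under section 6.3, Objective 1).** Uptake is "the number of men who will undergo VMMC divided by the number of uncircumcised men offered VMMC at the STI clinic", again with no venue. Each block is compared with SOC.
- **Time-to-uptake (same place, Objective 1a).** Here a venue is named: "the number of days taken for an individual to undergo circumcision at the VMMC clinic".
- **Referral and steering.** Under SOC, the mobilizer's morning session gives men slips to the VMMC clinic, about 300 metres away (section 6.2, Study setting). Escorts to that clinic are part of blocks two, three and four, and transport reimbursement is added in block four (section 6.6.2). Before reimbursement, "Documentation of the VMMC procedure will be confirmed in the VMMC" clinic's register (section 6.6.1).

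No follow-up contact or self-report is planned to find circumcisions done elsewhere. Section 6.5 (Limitations) does not mention incomplete or differential outcome capture.

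**The concern.** The defined outcome is any VMMC. Several operational statements point to counting only VMMC at the clinic, and the plan itself names the venues that fall in between. Men with symptomatic STIs cannot be circumcised on the day of their visit, so some leave and must return, and another venue could be used in that interval.

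A constant off-site loss would understate uptake everywhere but leave the ratio between phases intact. The trouble comes if the loss shrinks as the intervention builds up. An escort walks the man to the counted venue, and in block four payment depends on that venue's register. Both could move a circumcision from an uncounted place to a counted one without any additional man being circumcised. The comparison of blocks two to four with SOC would then favour RITE. The Kaplan-Meier comparison would be affected in the same direction, since an off-site circumcision would be treated as no event.

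**Working it through.** **The plan's own size figure.** Section 6.3 (Sample Size) gives 27 men per day, of whom 28% are already circumcised: 27 × (1 − 0.28) = 19.44, taken as 19 per day. Then 19 × 20 clinic days = 380 per month, and 380 × 6 = 2280. The stated figure reproduces. No power, target uptake or effect size is given.

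**Men per phase.** Section 6.6.2 expects blocks of 3-4 weeks. Assuming 5 clinic days per week, 19 × 5 × 3 = 285 and 19 × 5 × 4 = 380.

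**Model.** Let p be true uptake at any venue, the same in both phases, and q the share of circumcisions done off site and not captured (q0 under SOC, q1 in the block).

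- Measured uptake: a = p(1 − q0) under SOC and b = p(1 − q1) in the block.
- Apparent ratio: b/a = (1 − q1)/(1 − q0). If q0 = q1 the ratio is 1.
- Chance of a significant apparent increase, two-sided 0.05 (sidedness is not stated; two-sided is assumed): Φ[(b − a)/SE − 1.96], with SE = √[a(1 − a)/n + b(1 − b)/n]. At these sizes the planned t-test on a 0/1 outcome behaves like this normal test.

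**Results with p = 10%, n = 380 (p and q are assumptions)**

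| Off-site share, SOC vs block | Measured uptake | Ratio | SE | (b − a)/SE | Chance of false benefit |
|---|---|---|---|---|---|
| equal, e.g. 10% vs 10% | 9% vs 9% | 1.00 | 0.0208 | 0 | 2.5% |
| 10% vs 0% | 9% vs 10% | 1.11 | 0.0213 | 0.47 | 6.8% |
| 20% vs 10% | 8% vs 9% | 1.13 | 0.0202 | 0.49 | 7.1% |
| 30% vs 10% | 7% vs 9% | 1.29 | 0.0197 | 1.02 | 17% |
| 40% vs 10% | 6% vs 9% | 1.50 | 0.0191 | 1.57 | 35% |

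With 285 men per phase, the last three rows become 6.3%, 14% and 27%. Binomial simulation agrees with these values to within half a percentage point.

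**Sensitivity to true uptake (n = 380).** For shares of 20%, 30% and 40% falling to 10%, the chances are about 5%, 10% and 19% at p = 5%, and about 11%, 32% and 64% at p = 20%.

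**Which comparisons are exposed.** Block one adds education only, so this mechanism gives no reason for its off-site share to differ from SOC. Blocks two and three add the escort, and block four adds payment against the clinic register.

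**The case against.** The best defence is that section 6.2 (Study setting) already covers the point. It describes clinic, outreach and van circumcisions as the work of one service, says registers record referral source, and then says these registers will be used to trace STI-clinic referrals. On that reading the outreach and van procedures are included, and measuring at the facility describes only where data are abstracted. If so, the problem largely disappears. This stands as a possible reading. It is not stated, and the wording in sections 6.1 and 6.2 (Data Collection) pulls the other way.

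A reader might infer that the primary outcome is clinic-only as written. The documents do not establish that: the explicit venue limit belongs to Objective 1a, and the Objective 1 formula has none.

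A reader might also infer that SOC men are free to scatter across venues while RITE men are not. That overstates the contrast. Men who hear the mobilizer under SOC already receive slips to the same nearby clinic, and nothing in the documents shows that STI-clinic men use vans or outreach at all. Only a change in the off-site share matters, and it may be small.

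Finally, the cost of searching off-site registers depends on where they are kept and whether they can be linked, which the plan does not say.

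**Conclusion.** The point holds as a gap between the defined and the measured outcome that the plan should close. The venue-free definition, the off-site service and the clinic-centred measurement are all in the text. For time-to-uptake the clinic-only wording is explicit; for the primary outcome it is ambiguous.

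Bias in favour of RITE is possible in blocks two to four, with the strongest reason for it in block four, and only if off-site events are missed and their share falls relative to SOC. The documents do not support a claim that this bias is present, or that it affects block one.

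Its size cannot be derived from the plan. At an assumed 10% true uptake and 380 men per phase, the false-benefit rate runs from 2.5% with equal capture, through about 7% for a ten-point fall in the off-site share, to about 35% for a thirty-point fall (40% to 10%).

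**What to change.** - In section 6.1 (Study design), section 6.2 (Data Collection) and the Data Analysis text for Objectives 1 and 1a, state that uptake and time-to-uptake count VMMC at any venue of the programme, in line with section 4.
- Have the existing data clerks search clinic, outreach and mobile-van registers for STI-clinic referrals, with the same linkage in SOC and in every block. Set this before the SOC phase starts, since the comparison needs the same search throughout.
- Report uptake by venue, with clinic-only uptake as a sensitivity analysis.
- If the off-site registers cannot be reached, list differential outcome capture in section 6.5 (Limitations) and limit the conclusion to uptake at the clinic.

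The cost is some extra register look-up and linkage work. No study or clinical procedure changes. If the registers already include the off-site procedures, a sentence saying so, plus the table by venue, is enough.
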